8.5. Efficacy Analysis

The primary efficacy analysis will be performed to assess the Objective Response Rate (ORR) and secondary efficacy analysis will be performed to assess the PFS, overall survival rate and the best overall tumor response.

Inferential analysis results will be expressed as point estimates and their 95% CIs. Analyses will be carried out using SAS[®] Software, version 9.4 or higher (SAS Institute, Cary, North Carolina, USA).

All time-to-event endpoints, including OS and PFS, will be reported in days (median with 95% CI and range) and calculated using Kaplan-Meier methods. Subjects who have not progressed or who have not died at the time of the analysis will be censored at the last assessment date.

The study will be stopped early for futility if less than 1/10 showed ORR in Stage I; with no further investigation of the drug is less than 4/29 achieve ORR by the end of Stage II.

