I will provide all study personnel under my supervision copies of the protocol and access to all information provided by SynCore Biotechnology. I will discuss this material with them to ensure that they are fully informed about the drugs and the study.

I will conduct the trial in accordance with the guidelines of Good Clinical Practice (GCP) including the archiving of essential documents, the Declaration of Helsinki, any applicable local health authority, and Institutional Review Board (IRB) requirements.

Investigator Name (Printed)

Institution

Signature

Date

Please retain the original for your study files.

PROTOCOL SYNOPSIS

Name of Sponsor/Company: SynCore Biotechnology Co. Ltd.	
Name of Study Product: SCB01A	
Protocol Number: SCB01A-22	Indication: Recurrent or metastatic squamous cell carcinoma of head and neck
Title of Study: An open-label, phase II study to evaluate the efficacy and safety of SCB01A in subjects with recurrent or metastatic squamous cell head and neck cancer who have failed platinum-based treatment	
Study Center(s): Up to 4 centers in Taiwan	Study Development Phase: Phase II
Planned Number of Subjects: Up to 37 subjects will be enrolled, consisting of 10-13 subjects in Stage I and 19-24 subjects in Stage II, with replacement for those non-per protocol (non-PP) subjects (estimated 20% dropout rate).	

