Protocol Number: SCB01A-22	Indication: Recurrent or metastatic squamous cell carcinoma of head and neck

 • Response probability of null hypothesis (P0): 0.05 • Response probability of SCB01A (P1): 0.20 
According to these hypotheses, up to 37 subjects need to be recruited into the study (including 10 evaluable subjects in the Stage I and 19 evaluable subjects in Stage II, with the additional 8 subjects to account for replacement of subjects those who withdraw, i.e. dropout rate is 20%). At least 4 subjects are required to achieve CR or PR after treatment with SCB01A for the study to meet its primary objective. The trial will be discontinued if no objective response is observed after the Stage I tumor assessment review.
 
Stopping rule: stopped early for futility if less than 1/10 evaluable subjects showed ORR in Stage I; with no further investigation of the drug is less than 4/29 evaluable subjects achieve ORR by the end of Stage II.
 
Both according to ITT and PP approaches will be included in the efficacy analyses. The efficacy conclusion will be summarized according to analyses of PP population. Safety analysis will be done on ITT population. Inferential analysis results will be expressed as point estimates and their 95% confidence intervals (CIs). Analyses will be carried out using SAS[®] Software, version 9.4 or higher (SAS Institute, Cary, North Carolina, USA).
 
All time-to-event endpoints, including OS and PFS, will be reported in days (median with 95% CI and range) and calculated using Kaplan-Meier methods. Subjects who have not progressed or who have not died at the time of the analysis will be censored at the last assessment date.
 
PK Evaluations
 
The blood samples will be assayed for SCB01A and PK parameters (maximum plasma concentration [C_{max}], clearance [CL], volume of distribution [V_d], half-life [$t_{1/2}$], elimination constant [K_{el}], mean residence time [MRT] and time to maximum concentration [T_{max}]) will be determined and presented graphically and descriptively (as appropriate).
 
A detailed SAP will be finalized prior to final database lock. Any significant changes to the analyses described in this protocol will be addressed in the SAP and the Clinical Study Report.
	
Duration of the Study	
The planned duration of the entire study is approximately 26 months with an enrollment period of 12 months.	
End of Study	

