8.2. Determination of Sample Size

Assumption of sample size calculation:

- Study design: Simon's optimal two stage design¹
- Type I error (one-sided): 5%
- Power: 80%
- Response probability of null hypothesis (P0): 0.05
- Response probability of SCB01A (P1): 0.20

According to these hypotheses, up to 37 subjects need to be recruited into the study (including 10 evaluable subjects in the Stage I and 19 evaluable subjects in Stage II, with the additional 8 subjects to account for replacement of subjects those who withdraw, i.e. dropout rate is 20%). At least 4 subjects are required to achieve CR or PR after treatment with SCB01A for the study to meet its primary objective. The trial will be discontinued if no objective response is observed after the Stage I tumor assessment review.

Stopping rule: The study will be stopped early for futility if less than 1/10 evaluable subjects showed ORR in Stage I; with no further investigation of the drug is less than 4/29 evaluable subjects achieve ORR by the end of Stage II.

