#### 9.7.1.2 Statistical Analysis

Both ITT and PP approaches would be included in the efficacy analyses. The efficacy conclusion would be summarized according to analyses of PP population. Safety analysis would be done on ITT population. Inferential analysis results would be expressed as point estimates and their 95% confidence intervals (CIs). Analyses would be carried out using SAS® Software, version 9.4 or higher (SAS Institute, Cary, North Carolina, USA).

All time-to-event endpoints, including OS and PFS, would be reported in days (median with 95% CI and range) and calculated using Kaplan-Meier methods. Subjects who have not progressed or who have not died at the time of the analysis would be censored at the last assessment date.

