### Objective response rate (ORR) definition

ORR is defined as the percentage of subjects who have achieved confirmed CR and PR during treatment phase, according to RECIST v1.1. Not-confirmed CR or PR, or withdrawn for DLT are counted as non-responder. There are 5 subjects who are not evaluated due to clinical disease progression or AE/SAE. Tumor non-evaluable subjects are tend to be treatment failure and would also be counted as non-responder (not evaluable for response), instead of counted as missing.

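### Does leaving the ORR confidence-interval method unnamed, with no adjustment for the Stage I gate, need a change to the plan?

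*Protocol*

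**What the plan says.** The decision rule is a count. Protocol section 8.2 sets a Simon optimal two-stage design with null rate 0.05, target rate 0.20, power 80% and "Type I error (one-sided): 5" per cent. It enrols 10 evaluable subjects, stops if none responds, otherwise adds 19, and then "At least 4 subjects are required to achieve CR or PR after treatment with SCB01A for the study to meet its primary objective". Sections 8.5 and 8.7 repeat the two cutoffs.

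Reporting is described separately. Section 8.5 says "Inferential analysis results will be expressed as point estimates and their 95% CIs", and the Synopsis and SAP section 9.7.1.2 say the same. The only estimation method named is Kaplan-Meier, for PFS and OS. On the analysis set, SAP 9.7.1.2 adds: "The efficacy conclusion would be summarized according to analyses of PP population". Protocol sections 8.1 and SAP 9.7.1.3 refer to a detailed SAP to be finalised before database lock. The SAP text supplied covers only parts of sections 9.5 to 9.8, written in the style of a study report.

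**The concern.** With 29 subjects and few responders, binomial intervals differ noticeably from one method to another. If the method is picked once the data are known, that choice decides whether a trial declared successful at 4/29 shows an interval that includes or excludes its own null rate. The SAP's section on changes already reports patient data ("There are 5 subjects who are not evaluated due to clinical disease progression or AE/SAE"), so a choice made now could be called post hoc. The raw proportion also ignores that the trial continues only after at least one Stage I response, and this biases it. At stake are the readability of the headline result and a possible apparent contradiction between the count rule and the interval beside it.

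**Working it through.** **Inputs** (protocol 8.2, 8.5, 8.7): n1 = 10, stop at 0 responders; n2 = 19; success at 4 or more of 29; null 0.05, target 0.20, one-sided 5%.

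**1. The plan's own design.** P(success) is the sum over x ≥ 1 of P(X1 = x) × P(X2 ≥ 4 − x), with X1 ~ Bin(10, p) and X2 ~ Bin(19, p).
- At p = 0.05: 0.3151 × 0.0665 + 0.0746 × 0.2453 + 0.0105 × 0.6226 + 0.0010 = 0.0468.
- At p = 0.20: 0.8011.
- A search over all two-stage designs at these settings returns the same optimal design, 10 + 19 with cutoffs 1 and 4.

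**2. 95% intervals at 4/29 = 13.8%.**
- Wald: 0.1379 ± 1.96 × √(0.1379 × 0.8621 / 29) = 0.1379 ± 0.1255, giving 1.2% to 26.3%.
- Clopper-Pearson: the lower limit solves P(X ≥ 4 | 29, p) = 0.025 and the upper P(X ≤ 4 | 29, p) = 0.025, giving 3.9% to 31.7%.
- Jeffreys 4.8% to 29.5%; Agresti-Coull 4.9% to 31.2%.
- Wilson: (0.1379 + 0.0662 ± 0.1419) / 1.1325, giving 5.5% to 30.6%.
- Exact interval that respects the gate (stage-wise ordering): 4.1% to 34.3%.

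Of these, only Wilson excludes 5%. At 5/29 the Clopper-Pearson lower limit is 5.8%, so its overlap with the null is gone; Wald still includes 5% there (3.5%) and clears it at 6/29 (6.0%).

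**3. Why 5% lies inside.** The rule uses one-sided 5%, while a two-sided 95% interval corresponds to one-sided 2.5%. Adjusting for the gate does not remove the overlap at 95% (4.1%). Moving the gate-adjusted interval to 90% does: 5.1% to 30.8%, in line with the two-stage p-value of 0.0468. The main cause is the difference in level, and naming a method would not remove it.

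**4. How often it arises.** P(pass Stage I and total exactly 4) is 0.1201 at p = 0.20, which is 0.1201 / 0.8011 = 15% of successes. At p = 0.05 it is 0.0345. If Wald were used, 5/29 would be added: 0.1201 + 0.1619 = 0.282 at p = 0.20.

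**5. Is an ordinary exact interval valid despite the gate?** Use Clopper-Pearson on 0/10 for stopped trials and on s/29 otherwise, and sum the two-stage probabilities of the outcomes whose interval contains p. Coverage is 98.8%, 97.9%, 97.8% and 97.6% at p = 0.05, 0.10, 0.15 and 0.20. The minimum on a grid from 2% to 59% is about 93.9%.

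**6. Bias.** Let C = 1 − (1 − p)^10 be the chance of reaching Stage II.
- Raw rate given continuation: (10p/C + 19p) / 29. At p = 0.20: (2/0.8926 + 3.8)/29 = 0.2083, or +0.8 points. At p = 0.05: (0.5/0.4013 + 0.95)/29 = 0.0757, or +2.6 points.
- Raw rate over all trials, scoring 0/10 as zero: 0.8926 × 0.2083 = 0.186 (−1.4 points) and 0.4013 × 0.0757 = 0.030 (−2.0 points).
- The uniformly minimum-variance unbiased estimator (UMVUE; 16.5% at 4/29) averages p over all trials and is 0 at 0/10, so given continuation it averages p/C. At p = 0.20: 0.2241, or +2.4 points. At p = 0.05: 0.1246, or +7.5 points.
- Mean squared error over all trials, raw against UMVUE: 0.0023 against 0.0040 at p = 0.05; 0.0055 against 0.0063 at 0.10; 0.0077 against 0.0075 at 0.15; 0.0089 against 0.0081 at 0.20.

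**The case for a change.** The best case for acting is that it costs almost nothing. One sentence naming the method, fixed before anyone knows the response count, would end any suspicion of choosing between Wilson and Clopper-Pearson afterwards. A two-stage p-value with a 90% stage-wise interval would agree with the rule at 10 + 19. This matters most in borderline results: exactly 4/29 accounts for 0.0345 / 0.0468 = 74% of false successes at a true rate of 5%.

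Part of this stands. The method is absent from the text supplied, naming it would be tidy, and the stage-wise 90% interval is a reasonable labelled supplement. The rest does not carry. The count rule already decides success, so neither interval can rescue or sink the trial. Absence from the plan is not shown either, because the detailed SAP is a separate document and the supplied text begins mid-sentence.

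The argument that the headline ORR would be too low fails for the case raised. A trial reporting 4/29 has passed Stage I, and among such trials the raw rate is too high on average. The UMVUE enlarges that error about threefold (2.4/0.8 and 7.5/2.6 are both about 2.9).

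Nor do the enrolment ranges ("consisting of 10-13 subjects in Stage I and 19-24 subjects in Stage II") imply other stage sizes for the test. They include replacements for subjects outside the per-protocol set, and the evaluable numbers stay at 10 and 19.

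**Conclusion.** No change to the plan. The unnamed interval is a gap in detail that an analyst fills sensibly with an exact 95% interval, and that choice is valid under this design: coverage is 97.6% to 98.8% at true rates of 5% to 20%. The visible oddity, a successful trial whose 95% interval includes 5%, is confined with that interval to exactly 4/29 (probability 12.0% at a true rate of 20%). It reflects a one-sided 5% rule set beside a two-sided 95% interval, which is a matter of presentation. Estimators adjusted for the gate bring a trade-off: the UMVUE removes bias averaged over all trials, but it raises bias among trials that continue and has a larger mean squared error at true rates of 5% and 10%, with a smaller one at 15% and 20%.

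This rests on three assumptions: 10 and 19 evaluable subjects, the count rule alone deciding success, and an interval of ordinary quality. Wald would be a poor choice, because its overlap extends to 5/29 (28.2% in total at a true rate of 20%), but even then the trial's conclusion would not move. Intervals for the ITT set, or for any other denominator, would have different limits.

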6.1. Efficacy Measurements

Tumor response will be assessed by using computerized tomography (CT) or MRI scans according to RECIST v1.1 at baseline and at the end of Cycle 3 (at C3D21/EOT visit). For subjects who are continuing treatment beyond 3 cycles (9 weeks), tumor assessment will be performed at every three cycles until progression of disease (i.e. at or prior to Day 1 of Cycles 4, 7, 10 and so on). Any additional assessments can be arranged when clinically indicated.

Scans must include brain, chest, abdomen, and pelvis. The imaging technique used at baseline should be used throughout the study.

Subjects will be considered evaluable for tumor assessment in this study if they fulfill the criteria for evaluation according to RECIST v1.1, i.e., those subjects who undergo a baseline disease assessment within 4 weeks of treatment initiation, and who undergo at least 1 disease assessment on study (the following should be revised if revision in corresponding part in synopsis is accepted).

- ORR is defined as the percentage of subjects who have achieved confirmed CR and PR at a particular time point after first treatment, according to RECIST v1.1.
- PFS is defined as the time from the start of treatment up to the date of first progression based on RECIST v1.1 or the date of death, whichever comes first.
- OS is defined as the as the time from the start of treatment up to the time that the subject is still alive.
- Best overall tumor response defined as an objective response or stable disease of treatment phase.

Survival data will be collected throughout the active treatment phase and during the follow-up period. Survival follow-up after subject discontinuation of treatment will be conducted every 3 weeks during the first 9 weeks, thereafter every 9 weeks until the end of the study.

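### One shared censoring sentence for PFS and OS conflicts with the PFS definition: as written it would censor deaths without RECIST progression, and no single reading of it serves both endpoints

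*Protocol*

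**What the plan says.** Protocol section 6.1 (and the synopsis) sets the PFS endpoint: "PFS is defined as the time from the start of treatment up to the date of first progression based on RECIST v1.1 or the date". The definition goes on to name death as the alternative end point, taking whichever is earlier. Death is therefore a PFS event in its own right. The same section describes OS as the "time from the start of treatment up to the time that the subject is still alive", which does not name death as the event.

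Protocol section 8.5 sets the estimator: "All time-to-event endpoints, including OS and PFS, will be reported in days (median with 95% CI and range) and calculated using Kaplan-Meier methods". It then gives one censoring sentence for both endpoints: "Subjects who have not progressed or who have not died at the time of the analysis will be censored at the last assessment date". The synopsis repeats it, and SAP section 9.7.1.2 carries it over with only the tense changed: "Subjects who have not progressed or who have not died at the time of the analysis would be censored at the last assessment date".

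SAP section 9.8 lists exceptions and clarifications to the protocol analysis. Those shown concern PK handling and the ORR definition. Neither touches PFS or OS censoring.

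**The concern.** A PFS subject should be censored only if neither component of the endpoint has occurred. The sentence joins the two conditions with 'or' and does not separate the endpoints. A subject who dies without a documented RECIST progression has not progressed, so the sentence points to censoring while the definition points to an event.

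Such a record is realistic. The first scheduled post-baseline scan is at the end of Cycle 3, about week 9, and after that "tumor assessment will be performed at every three cycles until progression of disease". Once the end-of-treatment or early-withdrawal visit is past, the follow-up schedule (Protocol Table 3) collects survival status and cancer therapy but no scans. A subject who stops for toxicity or clinical decline and later dies falls into the conflict.

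These are poor outcomes, and censoring them moves PFS in the drug's favour. With no control arm, nothing inside the trial would offset that.

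**Working it through.** **The plan's own figures.** PFS and OS have no hypothesis, event target or power, so there is no figure to reproduce for them. The one design calculation is for ORR (Protocol section 8.2: P0 = 0.05, P1 = 0.20, one-sided 5%, power 80%, at least 1/10 and then at least 4/29). The probability of success is the sum over x = 1 to 10 of P[Bin(10, p) = x] × P[Bin(19, p) ≥ 4 − x]. It is 0.0468 at p = 0.05 and 0.801 at p = 0.20. Recruitment is 29/0.8 = 36.25, rounded up to 37. The design reproduces, and nothing below alters it.

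**Applying the sentence to each possible record.** Three readings are possible. *Literal*: censored if either condition holds. *By endpoint*: 'not progressed' governs PFS and 'not died' governs OS. *Neither*: censored only if both conditions hold.

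PFS:

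| Record | Definition (6.1) | Literal | By endpoint | Neither |
|---|---|---|---|---|
| Not progressed, alive | censored | censored | censored | censored |
| Not progressed, died | **event** | **censored** | **censored** | event |
| Progressed, alive | event | **censored** | event | event |
| Progressed, died | event | event | event | event |

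OS, taking death as the event:

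| Record | Should be | Literal | By endpoint | Neither |
|---|---|---|---|---|
| Not progressed, alive | censored | censored | censored | censored |
| Not progressed, died | event | **censored** | event | event |
| Progressed, alive | censored | censored | censored | **no rule** |
| Progressed, died | event | event | event | event |

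The literal reading fails both endpoints. The endpoint-by-endpoint reading is right for OS and wrong for PFS. The 'neither' reading is right for PFS and incomplete for OS. Changing 'or' to 'and' would therefore move the fault from PFS to OS.

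**Direction and size, under assumed inputs.** Let f be the share of first PFS events that are deaths without RECIST progression. The documents give neither f nor a PFS median. Assume exponential first-event times.

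1. *Event times known exactly, deaths censored on the day of death.* The median is multiplied by 1/(1 − f): 1/0.9 = 1.11 at f = 10%, and 1/0.7 = 1.43 at f = 30%.
2. *Progression dated to scans every 63 days, deaths censored at the preceding scan, assumed median 84 days, f = 30%.* The true event-free proportion is 2^(−63/84) = 0.5946 at day 63 and 2^(−126/84) = 0.3536 at day 126.
   - Deaths counted: the curve is 0.5946 − 0.30 × 0.2410 = 0.5223 just before day 126 and 0.3536 at day 126. The median is 126 days.
   - Deaths censored: at day 63, 1 − (0.70 × 0.4054)/(1 − 0.30 × 0.4054) = 1 − 0.2838/0.8784 = 0.677. At day 126, 0.677 × (1 − 0.1687/0.5223) = 0.458. The median is again 126 days, although the estimate at day 126 has risen from 35% to 46%.
3. *As in 2, with assumed median 60 days and f = 10%.* Deaths counted: 2^(−63/60) = 0.483 at day 63, so the median is 63 days. Deaths censored: 1 − (0.90 × 0.517)/(1 − 0.10 × 0.517) = 0.509 at day 63, so the median moves to the next scan, day 126.

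The curve is shifted upward each time, but the reported median may not move at all or may jump a whole scan interval.

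**The case against.** The strongest reply is that this is loose drafting, not a decision to censor deaths. The PFS definition is explicit. The literal reading would also censor every living progressor for PFS and every unprogressed death for OS, which nobody would intend. Protocol section 8.1 calls its text brief and leaves data conventions to a separate SAP, and the SAP text supplied itself refers to a detailed SAP, so endpoint-level rules may exist elsewhere. This stands as far as it goes: a reader might infer that deaths were in fact censored, and the documents do not support that, because they do not show which reading was programmed. It does not remove the conflict, because the less extreme endpoint-by-endpoint reading still censors the deaths, and the SAP text available repeats the sentence unrepaired.

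A reader might also try to size the effect from SAP section 9.8: "There are 5 subjects who are not evaluated due to clinical disease progression or AE/SAE". Taking 5/37 = 14% as the share of deaths without progression is not supported. The SAP does not say that any of the five died; 37 is the planned maximum, not the number treated; and a share of subjects lacking a tumour evaluation is not a share of first PFS events. Likewise, any percentage of PFS events lost under the literal reading needs the proportion of progressors alive at analysis, which is not given.

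The impact is also bounded. PFS and OS are descriptive secondary endpoints, and the go/no-go decision rests on ORR alone. In the PP set, a subject who dies before completing three cycles can enter only through DLT withdrawal, so early deaths bear mainly on the ITT estimate.

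**Conclusion.** The conflict is real and lies in the text: the shared censoring sentence contradicts the PFS definition under two of its three readings, and the third leaves a gap for OS. Whether any death was censored is not known. If the sentence is applied as written, the bias runs one way, towards longer PFS. Its size is undetermined: under the assumed inputs above, the median changes by anything from nothing to one 63-day scan interval, and those figures are illustration only. The ORR test, its error rates, the sample size and the stopping rule do not depend on this sentence. The point should be corrected before PFS is reported, but it does not threaten the primary conclusion.

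**What to change.** Replace the sentence in the synopsis, Protocol section 8.5 and SAP section 9.7.1.2 with two rules.

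- **PFS:** censor only subjects with neither RECIST progression nor death, at the last evaluable tumour assessment. A death without prior progression is an event on the date of death.
- **OS:** death from any cause is the event. Censor only subjects not known to have died, at the date last known alive, whatever their progression status. Amend the OS definition in the synopsis and section 6.1 to match.

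Confirm which reading was programmed, and rerun PFS and OS if it differs from these rules. The change needs no new data and leaves sample size, alpha and power as they are. Its one downside for the sponsor is that the reported PFS median may be less favourable.
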